Title of Protocol	CARAT: Canagliflozin vs. Placebo for Post BAriatric Patients with PeRsistent Type 2 DiAbeTes	
Principal Investigator / Study Sponsor	[name]	
Co-Investigators	[name] and [name]	
Mailing Address	Cleveland Clinic, [name]	
E-Mail Address	[contact]	
P.I.'s [contact]	[contact]
Funding Source	Janssen Scientific Affairs, LLC (Funding and Study Product) Cleveland Clinic Investigational Drug Service (IDS) Pharmacy (Placebo)	

PURPOSE OF PROTOCOL

Obesity is one of the greatest public health challenges of our nation and a leading risk factor for type II diabetes (DM2) development. Bariatric surgery is an effective therapeutic option for inducing marked weight loss and remission of DM2 (i.e., euglycemia without glucose lowering agents), which is supported by the publication of several randomized controlled trials (1-4). However, the variable durability of diabetes remission after surgery has been noted and is dependent on the extent of weight loss, degree of weight regain after the peak in weight loss, surgery type, and the duration of diabetes prior to surgery (5). An estimated ~20-40% of patients redevelop diabetes and require the addition of anti-diabetic agents within five years after gastric bypass despite achieving initial remission status (6-8). Consequently, there is a significant clinical need to identify evidenced based medical strategies to optimize the cardio-metabolic benefits of bariatric surgery, particularly for those with residual and/or recurrent DM2 (i.e., HbA1c \geq 6.5%) post-bariatric surgery.

Preliminary evidence from our randomized control trial of gastric bypass vs. sleeve gastrectomy (SG) vs. intensive medical therapy (IMT) for diabetes (STAMPEDE) indicates that diabetes non-remission (HbA1c >6.5%) at 24 months occurs in ~ 39% of post-gastric bypass patients with an average weight regain of ~5 kg (4). Recently, we have related diabetes remission status to improvements in pancreatic β -cell function, which is associated with greater weight/fat loss and elevations in adiponectin levels. Therefore, the aforesaid represent potential therapeutic targets with medical therapy in those who do not remit (9). Moreover, agents that act independently of insulin may be ideal for surgical non-remitters with poor residual beta cell function. For instance, canagliflozin, a novel class of antihyperglycemic agent, has been demonstrated to facilitate a favorable metabolic profile

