(i.e., weight loss and reductions in blood pressure without hypoglycemia) for patients with DM2 that may be ideally suited for post bariatric patients (10,11). *Thus, the purpose of this proposal is to evaluate the efficacy of canagliflozin in the post-operative management of DM2. We hypothesize that glucose lowering strategies that act independently of insulin and facilitate weight loss, will lead to better glycemic control and produce more favorable cardiometabolic changes than standard of care approach for post bariatric patients with persistent type 2 diabetes.* Therefore, the specific aims are:

1. Determine the clinical efficacy of canagliflozin vs. placebo in patients with type 2 diabetes post-bariatric surgery.

To test the clinical efficacy of canagliflozin in post bariatric patients (i.e., adjustable gastric banding [AB], Roux-en-y gastric bypass [RYGB] and sleeve gastrectomy [SG]) with type 2 diabetes, we will perform a randomized clinical trial of post bariatric surgery (>1 year) patients (N=36) and assign them into either a 6 month intervention of a) canagliflozin monotherapy (300mg qd) (N= 24) or b) placebo (N = 12). Including AB, RYGB, and SG subjects would give a more comprehensive understanding of the effects of canagliflozin, in the post-operative setting, given that they are the most common metabolic surgeries. The primary outcome measure is the change in Hba1c from randomization until 6 months in the medication group, relative to placebo. Secondary measures include the percentage of subjects who achieve glycemic control at 6-months (i.e., Hba1c <6.5%), fasting glucose, change in body weight, lipid, blood pressure control and symptomatic hypoglycemia episodes (per AE reporting).

2. Determine whether the cardiometabolic benefits of canagliflozin in post-bariatric individuals with diabetes is related to improvements in weight loss and adipokine (ie. adiponectin) levels.

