post-bariatric subjects enrolled in STAMPEDE trial: In forty subjects with residual type 2 diabetes (age 50yrs, HbA1c 8.2%, BMI 32 kg/m²) 32 months following gastric bypass and SG, 3 month use of generic phentermine (15mg) resulted in a decrease in HbA1c (8.4 ± 1.3 to 6.8 ± 0.8 , $P < 0.05$) and body weight by a median of 6.5kg. The use of basal insulin (0.3u/kg/day) resulted in less of a decrease in HbA1c (8.1 ± 1.4 to $7.3\% \pm 0.5$) and a median weight gain of 1.5kg.

Summary of Preliminary Data

These preliminary data from our institution demonstrate that relapse of diabetes control does occur with increasing time of follow up from gastric bypass procedure. Additionally, weight regain from nadir weight loss achieved after gastric bypass increases with time of follow up from surgery. Moreover, inadequate weight/fat loss and poor rise of adiponectin depict surgical non-remitters and these factors might be targeted with medical therapies to enhance greater weight/fat loss and increase adipose tissue health.

DESCRIPTION OF THE RESEARCH PROTOCOL

Experimental Plan: This is a prospective, randomized, double-blinded clinical trial for patients with recurrent type 2 diabetes post-gastric bypass surgery that will compare a 6 month course of canagliflozin monotherapy vs. placebo on clinical outcomes of type 2 diabetes. The rationale for including those subjects that initially remit but later redevelop as opposed to those that never achieve remission following metabolic surgery is based on several factors. Those that never achieve remission following metabolic surgery may not have had type 2 diabetes (but rather be autoimmune or MODY) prior to surgery or have the

ability to generate insulin from very poor residual β -cell function. Alternatively, those that initially remit have the potential to achieve durable remission in the future and may likely respond to adjunctive medical therapy. RYGB, AB, and SG operations comprise the majority of the bariatric practice and approximately 20-40% of those that initially remit may re-develop diabetes within a 5 year timeframe. Following consent and a screening visit to assess eligibility and clinical status (i.e. historical, physical and biochemical parameters including glycemic control and a pregnancy test in females), a baseline visit with diabetes educator will take place to provide standard diabetes education, nutrition and exercise prescription.

Sample Size Considerations

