Following randomization, subjects will be clinically evaluated at three office visits at 6 weeks, 3 and 6 months by PI and/or the research staff. The primary outcome measures at 6 months post-randomization include HbA1c followed by the change in HbA1c from randomization. Secondary measures include fasting glucose, BMI, change in body weight, blood pressure, lipid profile. Symptomatic hypoglycemia (blood glucose < 70) and drug related side effects (i.e. mycotic genital infections, urinary tract infection) will be monitored with adverse event reporting. Metabolic testing in all subjects at randomization and at 6

months will include a DXA scan for body fat composition and blood for leptin and adiponectin levels.

Rescue glucose lowering therapy will be provided for all subjects with a blood glucose >250 mg/dl. If chronic uncontrolled hyperglycemia (HbA1c $>11\%$) occurs then basal bolus insulin will be implemented. Subjects (20-75 years) who underwent AB, SG or RYGB within the past 15-years will be recruited. Including subjects who underwent surgery within the past 15-years will broaden the subject pool, as additional subjects who initially remitted and were subsequently rediagnosed will be identified. However, we will prioritize subjects who underwent metabolic surgery ≤ 6 years ago and who initially achieved remission status documented by HbA1c of $\leq 6.5\%$ within first year and a subsequent glycated hemoglobin $\geq 7.5\%$ (without any hypoglycemic agents) and less than 11% as upper limit. The rationale to prioritize patients that initially remit is that these patients have demonstrated ability to respond to surgical weight loss and subsequently redeveloped the disease. Whereas those that never achieved initial remission status may not respond to any intervention due to inexorable beta cell failure.

Initial recruitment will be achieved by a general awareness campaign, which will emphasize a study of methods of diabetes management post metabolic surgery. All patients will be pre-screened for inclusion and exclusion criteria by our clinical trial research nurse coordinator and/or research fellow. Evaluation of the inclusion and exclusion criteria, which are listed below, will occur both at the initial screening visit and the baseline visit, prior to randomization.

Statistical Methods

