Visit 3: Randomization visit with research coordinator and PI: Review of eligibility. Labs will be drawn for HbA1c, fasting glucose, lipid panel, uric acid, complete metabolic panel and adipokines (C-reactive protein, leptin, total and HMW adiponectin, leptin). Urine for albumin/creatinine ratio. DXA scan will be performed for body composition at this visit. Blood and urine will be collected for the bio-repository collection and is optional.

Visit 4: 6 week f/u visit: Research fellow/coordinator to assess adherence and safety.

Visit 5: 3 month visit with research coordinator and PI: Review of clinical status and biochemical labs will be drawn. These will include HbA1c and a complete metabolic panel.

Visit 6: 6 month visit with research coordinator and PI: Review of clinical status and biochemical labs will be drawn. These include HbA1c, fasting glucose, lipid panel, uric acid, complete metabolic panel and uric acid. Urine for albumin/creatinine ratio. Additionally, a DXA scan for body composition and blood for adipokines (C-reactive protein, total and HMW adiponectin, leptin) will be performed. Blood and urine will be collected for the bio-repository collection and is optional.

The window for all visits will be +/- 4 weeks.

Research Team: [name] is the principal investigator of this study and will consult with [name] (bariatric surgeon) for enrollment of appropriate candidates who underwent metabolic surgery at any Cleveland Clinic location, but that live within two hours of the Cleveland Clinic Main Campus. Both investigators have a long standing,

productive relationship. Statistical analysis will be provided by a Cleveland Clinic Quantitative Health Sciences statistician dedicated to endocrine and diabetes research. This team is well qualified to run post-bariatric trials and have successfully run two randomized control trial of bariatric vs. medical therapy for type 2 diabetes in obese patients.

POSSIBLE RISKS

Risks associated with Canagliflozin Include:

All drugs can cause unwanted effects called side effects. As of 28 September 2015 approximately 13173 subjects have received canagliflozin in completed or ongoing studies of 12 weeks or longer.

Side effects found in these studies that are more likely to occur with canagliflozin include those below. You should speak with your doctor about any changes to your diet or other medications you are taking:

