- **Amputation** of the toes (and to a lesser extent the foot or leg) could occur in up to 1 in 150 people per year on canagliflozin. This risk is greater in those with a prior history of amputation, disease of the circulation involving the legs or in those with nerve damage due to diabetes.
- **Decreased bone mineral density** - A clinical trial showed that canagliflozin caused greater loss of bone mineral density at the hip and lower spine than placebo.

Side effects in patients not involved in clinical studies who have been prescribed canagliflozin to treat their diabetes include those below. It is difficult to know specifically how often these side effects occur or always be certain if they are more likely to occur as a result of canagliflozin because these were not reported in the manner similar to data collection in a clinical study.

- Serious allergic reactions, including those with the symptoms of swelling of the face, throat, and/or tongue or breathing problems.
- Related to changes in lab tests associated with kidney function, severe cases of decreases in kidney function have been reported more commonly in patients who were dehydrated. Only subjects with an eGFR \geq 60mL/min will be enrolled into this study. While participating in this study, if a subject's lab results indicate a decline in eGFR between 45-60mL/min, the daily dose of canagliflozin will not exceed 100mg. If a subject's lab results indicate a decline in eGFR to <45mL/min, study medication will be withdrawn.
- Infections of the urinary tract that can spread to the kidneys or into the bloodstream.

Canagliflozin has been tested for its ability to cause harm to the fetus during pregnancy or cause birth defects. These studies have been done in animals. The studies that have been completed do not indicate that canagliflozin is associated with birth defects.

Nonetheless, women who are pregnant, lactating or intend to become pregnant during the study will be not allowed to participate in the study. Women who could possibly become pregnant

must have a negative pregnancy test prior to starting on the study drug and report immediately to the study site if they suspect they are pregnant during the study.

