- It becomes unlikely that any additional information can be obtained (subject or health care practitioner refusal to provide additional information, lost to follow-up after demonstration of due diligence with follow-up efforts)

All serious adverse events, pregnancy exposures and/or pregnancies in partners for Janssen medicinal products under study should be reported directly by the Sponsor Investigator, **within 24 hours of becoming aware**, to Janssen Scientific Affairs using the Janssen Scientific Affairs Serious Adverse Event Report Form. In the event the study is blinded, the Sponsor Investigator will submit an unblinded SAE or pregnancy exposure report to Janssen Scientific Affairs.

All follow-up information for serious adverse events that are not resolved at the end of the study or by the time of patient withdrawal must be reported directly by the Sponsor Investigator, **within 24 hours becoming aware**, to Janssen Scientific Affairs using the Janssen Scientific Affairs Serious Adverse Event Report Form.

VIII. Product Quality Complaints for Janssen Medicinal Products

A PQC may have an impact on the safety and efficacy of the product. Timely, accurate, and complete reporting and analysis of PQC information from studies are crucial for the protection of patients, investigators, and Janssen Scientific Affairs, and are mandated by regulatory agencies worldwide. Janssen Scientific Affairs has established procedures in conformity with regulatory requirements worldwide to ensure appropriate reporting of PQC information. Lot and/or Batch #s shall be collected or any reports of failure of expected pharmacological action (i.e., lack of effect).

All initial PQCs involving a Janssen product under study must be reported to Janssen Scientific Affairs by the Sponsor Investigator **within 24 hours after being made aware of the event**.

If the defect for a Janssen product under study is combined with either a serious adverse event or non-serious adverse event, the Sponsor Investigator must report the PQC to Janssen Scientific Affairs according to the serious adverse event reporting timelines. A sample of the suspected product should be maintained for further investigation if requested by Janssen Scientific Affairs.

IX. Maintenance of Safety Information

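### In a double-blinded trial, the principal investigator, as sponsor, is to send unblinded SAE reports, and nothing requires the causality opinion to be recorded first

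*Combined protocol and SAP*

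**What the plan says.** - **Blinding.** The Experimental Plan states: "This is a prospective, randomized, double-blinded clinical trial for patients with recurrent type 2 diabetes post-gastric bypass surgery".
- **One role.** The title block has a single entry for "Principal Investigator / Study Sponsor".
- **The unblinded report.** Adverse event reporting, section VII, has the Sponsor Investigator send all SAEs and pregnancy exposures directly to the funder within 24 hours, and adds: "In the event the study is blinded, the Sponsor Investigator will submit an unblinded SAE or pregnancy exposure report to Janssen Scientific Affairs". It sets no condition on relatedness, on expectedness, or on whether the subject's care needs the code.
- **Causality.** Section VII also has investigators enter in the CRF their view on whether an event is related to the funder's product. Section II.c lists relatedness and causality among the report fields. Neither says when the view is formed relative to opening the code.
- **Exposure exclusion.** Section I leaves out of reporting to the funder any subject who has not been exposed to the funder's product. The placebo is not the funder's: the title block credits "Cleveland Clinic Investigational Drug Service (IDS) Pharmacy (Placebo)".
- **Later contact.** After randomization, "subjects will be clinically evaluated at three office visits at 6 weeks, 3 and 6 months by PI and/or the research staff". The visit schedule also names the principal investigator at months 3 and 6, for example "Visit 6: 6 month visit with research coordinator and PI".
- **Leaving treatment or the study.** Section VI withdraws a subject who becomes pregnant. Under Possible Risks, "If a subject's lab results indicate a decline in eGFR to <45mL/min, study medication will be withdrawn". No text says that an SAE in itself ends participation.

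**The concern.** The causality opinion on an SAE is a judgment, and blinding is meant to protect it. Here the role that runs the trial and takes part in its visits also has to send a report that shows the treatment. If the code is opened to prepare that report before relatedness is entered, the opinion is given with the arm known, and the record will not show which came first.

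A subject who has an SAE and continues may be seen again by the same person, so later adverse event judgments on that subject would also be made with the arm known. At stake is the quality of some safety judgments in a small number of subjects. Events between consent and randomization are unaffected, because no arm exists yet.

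**Working it through.** The plan gives no figure on this point, so there is none to reproduce. The main check is to set the texts side by side.

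1. Section VII applies its rule when a study is blinded. The Experimental Plan says this one is, so the condition is met.
2. The rule names the Sponsor Investigator. The title block makes that role the principal investigator.
3. Section XI gives the Institution a share in transmitting SAEs, but it does not take the unblinded report away from the Sponsor Investigator. No text names a pharmacist or other unblinded person to add the arm, and there is no code-break procedure.
4. The section I exclusion does not avoid the problem. Deciding whether a blinded subject was exposed to the funder's product itself needs the code, and nobody else is assigned to check it.
5. The causality opinion could be entered while blinded, but no text requires that order.

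Next, how often this could happen.

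Inputs: 24 canagliflozin and 12 placebo subjects, 36 in all (aim 1 and Sample Size Considerations). The share p of randomized subjects with an SAE over 6 months is **assumed** to be 2%, 5% or 10%, equal in both arms, with subjects independent.

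Formulas: expected subjects = n × p; chance of at least one = 1 − (1 − p)^n.

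| Assumed p | n = 24: expected | n = 24: at least one | n = 36: expected | n = 36: at least one |
|---|---|---|---|---|
| 2% | 0.48 | 1 − 0.98^24 = 38% | 0.72 | 1 − 0.98^36 = 52% |
| 5% | 1.2 | 1 − 0.95^24 = 71% | 1.8 | 1 − 0.95^36 = 84% |
| 10% | 2.4 | 1 − 0.90^24 = 92% | 3.6 | 1 − 0.90^36 = 98% |

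The n = 24 columns are the firmer base. Section VII ties SAE reporting to the funder's products under study, and section I excludes unexposed subjects, so a placebo SAE may never be reported. The n = 36 columns apply if every SAE is reported, or if the principal investigator opens the code to find out whether a report is due.

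Finally, how far this could reach an outcome that partly rests on judgment. Aim 1 lists "symptomatic hypoglycemia episodes (per AE reporting)" as a secondary measure. If 5–10% of the affected subjects (a further assumption) later had an episode, the number exposed would run from 0.48 × 0.05 = 0.02 to 3.6 × 0.10 = 0.36 subjects in the whole trial, before any call was changed.

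**The case against.** The strongest reply is that little depends on this. Statistical Methods plans no comparison of SAE relatedness, and SAE counts by arm do not use it. The primary outcome is a laboratory HbA1c, and rescue insulin follows the same numeric thresholds in both groups. All of that stands, and it sets the severity.

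A second reply is that section VII says who submits the report, not who opens the code or fills in the treatment field. Section XI also involves the Institution, and the causality opinion belongs to investigators in the plural, so a blinded co-investigator could give it. This stands in part: it is the reason to say that the principal investigator is likely to learn the arm, not that this is certain. It does not remove the point, because the plan sets up no such separation.

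A reader might infer that symptomatic hypoglycemia would be biased in a particular direction, since section V says canagliflozin alone is not usually associated with it. The documents do not support that. Placebo alone carries the same low expectation, subjects are drug-naive or washed out, and the definition is anchored to a glucose below 70 with symptoms or a need for assistance. The arm sizes show how far one changed call would move a percentage, not how likely a changed call is.

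It is also fair to say that a full fix needs the funder's agreement, because section I presents these as the funder's requirements.

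**Conclusion.** The point holds as a low-severity weakness in safety reporting. The plan contains a rule that is likely to reveal the arm to the principal investigator for a reported SAE in a randomized subject, and it does not protect the causality opinion beforehand. The effect is confined to those opinions and to the principal investigator's later adverse event judgments in the few subjects who continue.

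It is fairly likely to happen at least once: 38–92% on the 24-subject base and 52–98% on 36. These ranges rest wholly on an assumed 2–10% SAE rate, equal by arm, with independent subjects. About 0.5 to 3.6 subjects would be affected. The ranges do not count pregnancy reports.

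A reader might infer that the primary comparison is compromised or that the trial is not truly blinded. The documents support neither. The effect on HbA1c is negligible, and nothing here unblinds subjects without a reported SAE or pregnancy exposure.

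**What to change.** Amend section VII as follows:

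- The investigator records and dates relatedness in the CRF and sends the SAE report within 24 hours while blinded, giving the treatment as canagliflozin or placebo.
- The investigational pharmacy, or another delegate with no part in visits or causality, sends arm and dose to the funder within the same 24 hours and applies the section I exposure exclusion. The documents say only that the pharmacy supplies placebo, so its access to the code must be confirmed.
- The principal investigator opens the code only when the subject's care requires it, with date and reason logged.
- The SAE listing that the funder returns at least quarterly (section XII) goes to the delegate. Otherwise, a list confined to canagliflozin cases would itself reveal the arm.

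If the funder will not accept a separate sender, at minimum require the causality opinion to be dated before the code is opened. That adds one dated CRF entry, but it protects only the causality opinion and not later judgments on the same subject.

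The cost of the full version is a short code-handling instruction, the funder's agreement, and one extra message per SAE: about 1 to 4 in all if every SAE is reported, at the assumed rates and one SAE per affected subject. The funder still has the unblinded information within 24 hours.
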